## LIST OF ABBREVIATIONS AND DEFINITION OF TERMS

AE	Adverse Event
ALP	Alkaline Phosphatase
ALT	Alanine Transaminase
ANC	Absolute number of neutrophils
aPTT	Activated Partial Thromboplastin Time
AST	Aspartate Transaminase
AUC	Area Under the Curve
BP	Blood Pressure
BUN	Blood Urea Nitrogen
CBC	Complete Blood Count
CMP	Comprehensive Metabolic Panel
CNS	Central Nervous System
ConMeds	Concomitant medications
CRF (eCRF)	Case Report Form (Electronic Case Report Form)
CRO	Contract Research Organization
CSR	Clinical study report
CT	Computed Tomography
DLT	Dose Limiting Toxicity
DNA	Deoxyribonucleic acid
DP	Drug Product
ECG	Electrocardiogram
ECOG	Eastern Cooperative Oncology Group
EDC	Electronic Data Capture
EOS	End-of-Study
EOT	End of Treatment
FDA	Food and Drug Administration
GCP	Good Clinical Practice
G-CSF	Granulocyte Colony-Stimulating Factor
GI	Gastrointestinal
GLP	Good Laboratory Practice

---

GMP	Good Manufacturing Practice
H1	Histamine-1
HbcAb	Hepatitis B core antibody
HBsAg	Hepatitis B Surface antigen
HBV	Hepatitis B virus
HCV	Hepatitis C virus
HIV	Human immunodeficiency virus
HNSTD	Highest noseverely toxic dose
HR	Heart rate
IB	Investigator's Brochure
IBD	Inflammatory Bowel Disease
IC50	Half maximal inhibitory concentration
ICF	Informed Consent Form
ICH	International Conference on Harmonization
IEC	Independent Ethics Committee
IgG	Immunoglobulin G
INR	International Normalized Ratio
IRB	Institutional Review Board
IRR	Infusion Related Reaction
IUD	intrauterine device
IUS	Intrauterine system
IV	Intravenously
IVIG	IV immunoglobulin
MCH	Mean Corpuscular Hemoglobin
MCHC	Mean Corpuscular Hemoglobin Concentration
MCSF	Macrophage Colony-Stimulating Factor
MCV	Mean Corpuscular Volume
MedDRA	Medical Dictionary for Regulatory Activities
MRI	Magnetic Resonance Imaging
MRSD	Maximum Recommended Starting Dose
Nabs	Neutralizing antibodies

NYHA	New York Heart Association
PDF	Portable Document Format
PDX	Patient derived xenograft
PE	Physical examination
PET	Positron emission therapy
PK	Pharmacokinetics
PT	Prothrombin time
QA	Quality assurance
QC	Quality control
QTcF	QT-interval corrected according to Fridericia's formula
RBC	Red blood cells
RDW	Red Cell Distribution Width
REB	Research Ethics Board
RNA	Ribonucleic acid
SAE	Serious Adverse Event
SMP	Study Monitoring Plan
SOC	System organ class
SOP	Standard Operating Procedures
SPR	Surface plasma resonance
SRC	Safety Review Committee
SUSARs	Suspected Unexpected Serious Adverse Reactions
TCR	Tissue cross-reactivity
TEAE	Treatment Emergent Adverse Event
TK	Toxicokinetics
ULN	Upper Limit of Normal
UPCR	Urine Protein to Creatinine Ratio
WBC	White Blood Cells

## 1 PROTOCOL SUMMARIES

### 1.1 Synopsis

Title:	A Phase 1 randomized, double blinded, placebo-controlled single dose escalation study of OsrHSA in adult healthy male and female volunteers
Sponsor:	Wuhan Healthgen Biotechnology Corporation
Study Drug:	OsrHSA (Recombinant Human Albumin from Oryza sativa ) for infusion  Normal Saline (0.9% Sodium Chloride) will be used as the placebo
Clinical Trial Phase:	Phase 1
Proposed Indication:	Circulatory dysfunction due to hypovolemia, including patients with cirrhotic ascites and hypoalbuminemia
Primary Objectives:	

To assess the safety and tolerability profile of OsrHSA when administered as single dose IV infusion

Secondary Objectives:	

To characterize the pharmacokinetics (PK) of OsrHSA when administered as single dose IV infusion

immunogenicity profiles of OsrHSA when administered as single dose IV infusion

Exploratory	To assess changes in serum albumin level, colloid osmotic pressure, blood pressure and body weight when

Objectives:	administered as single dose IV infusion
Study Population:	Healthy male and female volunteers, non-smokers, 18-55 years of age
Number of Subjects planned:	Up to 40 subjects, additional subjects might be recruited depending on emerging data from current study and the ongoing trial in China
Number of Study Centers Planned:	One study site located in the United States
Study Design:	
This is a Phase 1 randomized, double blinded, placebo-controlled, single dose escalation study to evaluate safety, tolerability, PK, and immunogenicity of OsrHSA in healthy volunteers (See study design schema).
 
After a screening period of up to 28 days, the qualified subjects will be randomized to OsrHSA or placebo (6:2). Each enrolled subject will receive one single assigned dose of OsrHSA or placebo. The investigator and subjects will be blinded to treatment assignment. During the study, subjects will be evaluated for safety and tolerability, PK/PD, and activity of OsrHSA.
 
On day 1, OsrHSA or placebo will be administered as single IV infusion at a rate lower than 2 ml/min to the subjects. Patients will be observed overnight. On Day 2, after completion of the study procedures and assessments, subjects will be discharged from the clinical research center. Seven-day dose-limiting toxicity (DLT) observational period will commence upon completion of dosing at the end of infusion (EOI). Subjects will have end-of-study (EOS) follow-up visits on Day 30 after infusion.
 
The planned doses are 20, 40, 80, 140, and 200 mg/kg, dose level(s) higher than 200mg/kg might be an option(s) based on emerging data from this study and ongoing China clinical trial (China IND#: CXSL1500135; Protocol Number: HY1001) .

Dose escalation decisions will be determined based on toxicities data as well as available all available PK data observed within 7 days after dosing.

**Study participation  
Duration:**

The screening period is up to 28 days, one treatment day, and follow-up period of 30 days

**Pharmacokinetic (PK)  
evaluations:**

Blood samples for single dose PK will be collected from all subjects to determine the albumin concentration changes, they will be taken at time points listed in [Table 1](#). The PK of OsrHSA will be analyzed using standard non-compartmental analysis (NCA) by validated software WinNonLin version 6.4 or higher (Certara, NJ, USA). PK parameters derived from NCA analysis will include, but not limit to,  $AUC_{0-\infty}$  and  $AUC_{0-t}$ ,  $C_{max}$ ,  $t_{1/2}$ , CL, and  $V_d$ . PK parameters will be listed for each subject and summarized with descriptive statistics by each dose level/cohort. PK parameters will also be presented with baseline corrected.

Blood samples for immunogenicity will be collected at time points shown in [Table 1](#). Neutralization activity will be evaluated if ADA is positive.

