#### 4.2.1 Definition of Dose Limiting Toxicity (DLT):

AEs will be graded according to the FDA Guidance for Industry *Toxicity Grading Scale for Healthy Adult and Adolescent Volunteers Enrolled in Preventive Vaccine Clinical Trials*. DLT is

defined according to the criteria below as any TEAEs occurring during the DLT observation period (7 days) and considered to be related to OsrHSA:

*Any Grade  $\geq$  3 AE or laboratory abnormality as defined in the FDA Guidance for Industry Toxicity Grading Scale for Healthy Adult and Adolescent Volunteers Enrolled in Preventive Vaccine Clinical Trials*

All Grade 3 toxicities for vital signs and laboratory parameters must be confirmed with a repeat measurement obtained within 1 hour or as soon as possible for vital signs and within 24 hours for laboratory parameters.

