#### **4.2.2 Dose-escalation Criteria:**

Tolerability and safety of subjects in a cohort will be reviewed by the SRC which is comprised of an independent Medical Monitor, site Principal Investigator, and Sponsor Study Director. Dose escalation may be stopped at any time based upon the Sponsor or Investigator's clinical assessment or judgment. Upon completion of the DLT observational period (first week after dosing), the SRC will examine safety data through Week 1 for each dose cohort in combination with all available, previously accumulated safety data, as well as available PK data, if any, from all subjects enrolled in the study to date. All cohorts will enroll 8 subjects (safety data from at least 6 or 7 subjects would be needed for SRC meeting, in case a subject discontinues the study), if no more than 2 out of 8 subjects experiences DLT as defined in the section 4.2.1, dose will be escalated to the next dose level.

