#### **4.2.3 Subject Stopping Criteria:**

Dosing will be permanently stopped for any individual subject experiencing any of the following:

- Any SAE, regardless of causality to the study drug.

- Subject experience DLT.
- Hypersensitivity or anaphylactic reaction following start of infusion.
- Medical condition that is judged by the Investigator as to jeopardize the subject's safety if he or she continues to receive the study drug.
- QTc prolongation defined as QTcF increasing  $\geq 60$  msec and persisting for at least 10 minutes or QTcF  $> 500$  msec and persisting for at least 30 minutes, or episode of torsade de pointes.

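### The DLT window opens at end of infusion, so a related Grade ≥3 event that starts and resolves during the infusion is not a DLT and the DLT stopping rule cannot stop an infusion

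*Combined protocol and SAP*

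**What the plan says.** **Window.** The synopsis (1.1) states: "Seven-day dose-limiting toxicity (DLT) observational period will commence upon completion of dosing at the end of infusion (EOI". Section 4.2.2 places it in the same way: "Upon completion of the DLT observational period (first week after dosing), the SRC will examine safety data through Week 1".

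**DLT definition.** Section 4.2.1 confines DLTs to "any TEAEs occurring during the DLT observation period (7 days) and considered to be related to OsrHSA", at Grade 3 or above. A Grade 3 vital sign "must be confirmed with a repeat measurement obtained within 1 hour or as soon as possible for vital signs".

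**Subject stopping rule.** Section 4.2.3 opens: "Dosing will be permanently stopped for any individual subject experiencing any of the following". Five bullets follow: any SAE; "Subject experience DLT"; "Hypersensitivity or anaphylactic reaction following start of infusion"; a medical condition that the Investigator considers a danger to the subject; and QTcF prolongation or torsade.

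**Dosing.** Each subject receives one dose (4.2, 6.3), infused over 2 h ± 20 min (6.2.4).

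**Escalation.** Section 4.2.2 escalates "if no more than 2 out of 8 subjects experiences DLT as defined in the section 4.2.1". Section 4.2.4 withholds escalation when at least 2 of 8 subjects have Grade 3 or higher toxicity, with no time window and no causality condition. Its first criterion also withholds escalation when at least 2 subjects in a cohort meet a 4.2.3 rule and the Investigator sees a similar risk for the others.

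**The concern.** A DLT cannot exist until the infusion has ended, and by then nothing of the single dose is left to withhold. The DLT bullet in 4.2.3 therefore cannot do what the opening sentence of that section says it does. The list is evidently meant to act during the infusion: the hypersensitivity bullet next to it runs from the start of infusion, and in a single-infusion study there is no other time at which dosing can be stopped.

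Two things are at stake. The first is whether a stated rule, or only judgment, ends the infusion of a subject with a related Grade 3 event. The second is whether that event enters the DLT count that the Safety Review Committee (SRC) uses under 4.2.2. The infusion is also the most closely watched part of the study, with blood pressure taken every 10 minutes (1.3, footnote 6).

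**Working it through.** **Step 1. Length of the uncovered interval.** Inputs from 6.2.4 are a volume of 200 ml, a rate below 2 ml/min and a stated time of 2 h ± 20 min. Time = volume / rate. At the cap, 200 / 2 = 100 min, which is the lower limit of the stated range. At 120 min the rate is 200 / 120 = 1.67 ml/min, and at 140 min it is 200 / 140 = 1.43 ml/min. The stated time reproduces: the interval outside the DLT window is 100 to 140 min.

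**Step 2. What each 4.2.3 bullet can do.**

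| Bullet | Can stop a running infusion | Can count towards 4.2.4, first criterion |
|---|---|---|
| SAE | Yes | Yes |
| DLT | No: none can exist before end of infusion | Yes, if it occurs after the infusion |
| Hypersensitivity | Yes | Yes |
| Investigator judgment | Yes | Yes |
| QTcF | Yes | Yes |

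**Step 3. Which events fall in the gap.** Start from related Grade ≥3 events during the infusion and remove those that are covered elsewhere.
- Grade 4 is the potentially life-threatening grade (10.3). Such an event would generally meet the SAE definition in 10.1, so the SAE bullet applies.
- Hypersensitivity and QTcF prolongation have their own bullets.
- Table 1 schedules no hematology or chemistry between pre-dose and 0.5 h after end of infusion, so laboratory DLTs are not expected in the interval.
- An event that continues past end of infusion can be read as occurring in the window.
- A Grade 3 vital sign that the repeat measurement does not confirm is not a DLT under either window.

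What remains is a non-serious Grade 3 symptom, or a confirmed Grade 3 vital sign, that is over by end of infusion.

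**Step 4. Effect on the numeric escalation limits.** Let j be the number of subjects whose only related Grade ≥3 event is confined to the infusion, and m the number with such an event after it, with j + m ≤ 8. The number of (j, m) pairs is 1 + 2 + … + 9 = 45. Escalation is taken as withheld if either section withholds it, before any unblinded reassessment.
- As written: hold if m ≥ 3 (4.2.2) or j + m ≥ 2 (4.2.4).
- Window from start of infusion: hold if j + m ≥ 3 (4.2.2) or j + m ≥ 2 (4.2.4).

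Both reduce to j + m ≥ 2. Escalation proceeds only at (0,0), (1,0) and (0,1) and is held at the other 45 − 3 = 42 pairs, under either window. The decisions differ in 0 of 45.

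Under 4.2.2 alone they differ when m ≤ 2 and j + m ≥ 3. That is j = 3 to 8 for m = 0, j = 2 to 7 for m = 1 and j = 1 to 6 for m = 2, or 6 + 6 + 6 = 18 pairs. Section 4.2.4 already holds escalation in all 18.

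**Step 5. What the count leaves out.** Section 4.2 says escalation goes on without interruption while no DLT or stopping criterion is met. Read literally, a single infusion-only event does not interrupt escalation now and would do so under the wider window. The weight of this is limited, because 4.2.2 tolerates up to two DLTs. The count also leaves out a cohort in which one subject has an infusion-only event and another meets a different 4.2.3 rule without a Grade ≥3 event. There the first criterion of 4.2.4 could see one subject where the wider window would give two, though it also requires the Investigator to see a risk of similar reactions.

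**The case against.** The strongest reply is that little is lost. Four of the five bullets work during the infusion. Section 6.2.4 requires monitoring for infusion-related events and provides for interrupting an infusion that is not tolerated, and 6.4.1 allows removal for an adverse event or safety concern. Adverse events are recorded from the start of dosing (7.1) and summarised by severity and relationship (11.4.2), and the SRC sees all accumulated safety data (4.2.2). The DLT bullet may simply be wording carried over from a multiple-dose design. All of this stands, and it limits the size of the point. It does not make the DLT bullet able to stop an infusion.

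A second reply is that stopping an infusion early brings end of infusion forward, so an event still present becomes a DLT. That may be so, although the protocol does not link early termination to the DLT clock. The DLT would then follow from the stop and could not have been the reason for it.

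Three stronger readings are tempting, and the documents do not support them.
- *A reader might infer that the DLT bullet is wholly dead.* It is not: a post-infusion DLT meets 4.2.3 and feeds the first criterion of 4.2.4. Only the stop-dosing action is empty. After the infusion the SAE, hypersensitivity and QTcF bullets have nothing left to stop either.
- *A reader might infer that infusion reactions escape review, or that a cohort with several of them could escalate unnoticed.* Step 4 and the recording rules in 7.1 show otherwise.
- *A reader might infer that incomplete infusions are not provided for at all.* Sections 4.2, 6.2.4 and 6.4.3 cover interruptions and partial doses. Only the tie to the DLT period is missing.

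**Conclusion.** The point holds, and it is minor. As written, no event confined to the 100 to 140 min infusion can be a DLT, and the DLT bullet of 4.2.3 cannot end an infusion. In practice this affects the narrow class of events left after step 3, of which a transient Grade 3 blood pressure rise is the natural example. For these, stopping depends on the Investigator and not on a stated rule, and the DLT count omits them.

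The combined numeric limits of 4.2.2 and 4.2.4 are unaffected. The documents give no rate for such events, so no probability is attached.

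The conclusion assumes that the synopsis start time governs, that 4.2.4 prevails where it is stricter than 4.2.2, and that no other text opens the window earlier. The schema in Figure 1, section 2.2 and part of 4.3 could not be checked. If any of them starts the period at the start of infusion, the point becomes an inconsistency with 1.1, and the same edit resolves it.

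**What to change.** In 1.1 and 4.2.1, define the DLT period as beginning at the start of infusion and ending 7 days after end of infusion, or 7 days after early termination of the infusion. Have 4.2.2 and 10.9 refer to that definition in place of their own descriptions of the first week.

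The cost is one sentence and two cross-references. No new data are needed, because adverse events and blood pressure during the infusion are already collected. The timing of SRC review does not move, since the period still closes 7 days after end of infusion. The one operational consequence is that a confirmed, related Grade 3 event during dosing would require the infusion to be stopped, with replacement available under 6.4.3. That is what 4.2.3 already says it intends.

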**Efficacy Evaluations:**

The parameters including, but not limited to, serum albumin level, colloid osmotic pressure, blood pressure, 24-hour fluid input and urine output, and body weight will be measured at baseline and at time points listed in [Table 1](#). The changes in serum albumin level, colloid osmotic pressure, blood pressure, body weight and other parameters will be assessed.

[figure not shown]
**Immunogenicity:** Blood samples for immunogenicity will be collected until 30 days after the infusion

**Statistical Analysis:** All PK, immunogenicity, safety and efficacy data will be summarized using descriptive statistics (number of subjects, mean, median, standard deviation, minimum, and maximum) for continuous variables and using frequencies and percentages for discrete variables.

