### OsrHSA Phase 1 study design schema

### 1.3 Schedule of Activities

- a. Screening procedures will be performed at screening visits from D-28 to D-2, including ultrasound, smoking, alcohol, drug use test, serum albumin. Pre-dose from D-1 to infusion, smoking, alcohol, drug use test, serum albumin will be performed again. (The two times serum albumin average will be used as subject's baseline serum albumin)
- b. Urine collection will be performed 24hr after infusion
- c. The 0.5h time point after dose initiation will change to  $\pm 5$  minute window (instead of  $\pm 2$  minute).
- d. The D3 and D5 time points will change to  $\pm 6$  hour window (instead of  $\pm 4$ h)
- e. Abdominal ultrasound exam will be performed and reviewed during the 28 day screening period, prior to patient check-in on Day -1
- f. Alcohol and Cotinine will be tested at all follow-up visits (D3, D5, D8, D15, D22, D30)
- g. Syphilis will be tested at the screening timepoint, in order to adhere to the new exclusion criteria described above
- h. Anti-HCP antibody will be measured at the same time points as ADA
- i. In order to calculate accurate creatinine clearance, subjects' body weight will be re-measured at Day 8 and Day 30 visits.
- j.

Table 1 Schedule of Activities

Protocol Activity	Clinical Research Unit (CRU) Confinement										Outpatient Visits					
	Screen -D28 to -D2	Pre-dose -D1 to dose	Dose initiation	0.5 h $\pm$ 5m after Dose initiation	1.0h $\pm$ 10m after Dose initiation	EOI+ 10m	0.5h Post EOI $\pm$ 10m	4h $\pm$ 10m	12h $\pm$ 10m	D2 24h $\pm$ 30m	D3 $\pm$ 6h	D5 $\pm$ 6h	D8 $\pm$ 1d	D15 $\pm$ 2d	D22 $\pm$ 2d	D30 $\pm$ 2d
Signed Informed Consent (ICF) 	×															
Inclusion/Exclusion Criteria	×	×														

Protocol Activity	Clinical Research Unit (CRU) Confinement										Outpatient Visits					
	Screen -D28 to -D2	Pre-dose -D1 to dose	Dose initiation	0.5 h ± 5m after Dose initiation	1.0h ± 10m after Dose initiation	EOI+ 10m	0.5h Post EOI ± 10m	4h ± 10m	12h ± 10m	D2 24h ± 30m	D3 ± 6h	D5 ± 6h	D8 ± 1d	D15 ± 2d	D22 ± 2d	D30 ± 2d
Demographics 	×															
Weight 	×	×							×	×		×				×
Medical History 	×	×								×	×	×	×	×	×	×
Physical Examination 	×	×				×	×	×	×	×	×	×	×	×	×	×
Current Medications/OTC/supplements	×	×											×			×
Vital Signs 	×	×		×	×	×	×	×	×	×	×	×	×	×	×	×
12 Lead Electrocardiogram (ECG) 	×	×			×	×	×	×	×	×	×	×	×	×	×	×

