6. Vital signs include temperature, pulse, respiratory rate, and blood pressure. Vital signs will be assessed at screening and on the visits at the clinical research unit. Vital sign will be performed within 30 minutes prior to the infusion, at the EOI (+ 5 minutes) and before every PK sampling. Additionally, blood pressure will be measured every 10 minutes during infusion, every 30 min post EOI up to 6 hours, every 1 hour after 6 hours up to 12 hours post EOI, and every 2 hours until 24 hours post EOI or discharge, and at every outpatient visit. Blood pressure should be measured prior to Colloid osmotic pressure sampling when blood pressure measuring and colloid osmotic pressure sampling are specified to be done at the same time.
7. ECGs (12 lead) will be collected at screening, predose, during infusion(1hr),and EOI, prior to PK sampling during Day 1, and as clinically indicated, and at EOS.
8. Abdominal ultrasound exam will be performed and reviewed during the 28 day screening period, prior to patient check-in on Day -1
9. Only in women of childbearing potential. Urine pregnancy test will be done at screening and EOS, serum pregnancy test will be done pre-dose and on D15, or as clinically indicated.
10. Hematology includes Complete blood count (CBC) (hematocrit (HCT), hemoglobin, red blood cells (RBC), Red Cell Distribution Width (RDW), Mean Corpuscular Volume (MCV), Mean Corpuscular Hemoglobin (MCH), Mean Corpuscular Hemoglobin Concentration (MCHC), platelets, white blood cells (WBC) with absolute differential counts of neutrophils, lymphocytes, monocytes, eosinophils, and basophils). Serum Chemistry ALT, AST, ALP, K+, Na+, Cl-, Ca2+, TBIL, blood urea nitrogen (BUN) or urea, creatinine, uric acid, glucose (non-fasted).
11. HIV screening (Antigen/antibody test), HCV antibodies, hepatitis B surface antigen (HBsAg), hepatitis B surface antibody (anti-HBs), total hepatitis B core antibody (anti-HBc), IgM antibody to hepatitis B core antigen (IgM anti-HBc), Syphilis.
12. Twenty-four hours urine for D1 after the administration will be collected for 24 hours urine protein. Dipstick is acceptable for other time points. Microscopic analyses if clinically indicated. If  $\geq 2+$  protein on urine dipstick, then collect spot urine sample to calculate urine protein to creatinine ratio (UPCR) or collect 24h urine.

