13. PK samples (Serum albumin) will be collected at pre-dose, 0.5h after dose initiating, EOI, and 0.5h, 4h, 12h, 24h (Day 2), 48h (Day 3), Day 5, Day 8, Day 15, Day 22, and Day 30 post EOI. The exact/actual time to collect blood will be documented.
14. Colloid osmotic pressure will be measured within 30 min predose, every 30 min after dose initiating until EOI, EOI, every 1 hour up to 6 hours post EOI, every 2 hour after 6 hours up to 12 hours post EOI, and every 4 hours until 24 hours post EOI or discharge, 48h (D3), D5, D8, D15, D22, and D30 post EOI. Blood pressure should be measured prior to each colloid osmotic pressure sampling.
15. Blood samples for ADA and Anti-HCP antibody analyses will be collected at pre-dose, D8, D15, D22, and D30 post EOI.

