##### Exploratory Endpoints

- Changes in serum albumin level and colloid osmotic pressure
- Changes in body weight and blood pressure

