#### **6.2.4 Treatment Allocation and Administration, Dosing Regimen**

This is a Phase 1 randomized, double blinded, placebo-controlled study. Subjects will be randomized. Both subjects and investigator will be blinded.

[figure not shown]
1. Parenteral drug products should be prepared by using appropriate aseptic technique, and inspected visually for particulate matter and discoloration prior to administration, whenever solution and container permit.

2. Treatment Allocation and Administration: OsrHSA will be diluted with normal saline to a total volume of 200ml.

The total infusion time will be 2hr ± 20min.

The OsrHSA infusion rate is lower than 2ml/min. The procedures used for administration are following:

- First, set up intravenous channel and intravenous injection of 50 ml saline. The infusion rate for normal saline will be 5ml/min.
- Second, OsrHSA or placebo will be administered via an infusion line equipped with a 0.2µm in-line filter. And monitor for infusion-related AEs during administration. The rate of intravenous should be lower than 2 ml/ min and cautions should be taken. Dose interruption based on intolerability will be captured in the monitoring of infusion start and stop times.
- Third, flush with 50ml normal Saline after the dose. The infusion rate for normal saline will be 5ml/min.

All dose administrations will be performed in the clinical center under the supervision of appropriately trained staff.

Further detailed instructions on handling and administration of study drug is described in the separate Pharmacy Manual.

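### The PK analyte is named as serum albumin in some places and OsrHSA in others, with assay specificity unstated, and section 11.4.1 does not say whether baseline-corrected values are primary or enter the power model

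*Combined protocol and SAP*

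**What the plan says.** **Analyte.** The synopsis (1.1, PK evaluations) states: "Blood samples for single dose PK will be collected from all subjects to determine the albumin concentration changes". Footnote 13 of Table 1 begins: "PK samples (Serum albumin) will be collected at pre-dose, 0.5h after dose initiating, EOI", and continues to Day 30. Section 7.2 instead has serum OsrHSA measured by a validated immunoassay, and section 11.4.1 plots OsrHSA concentrations. The synopsis itself also refers to the PK of OsrHSA when it introduces the non-compartmental analysis (NCA).

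**Baseline.** After listing the NCA parameters, the synopsis adds: "PK parameters will also be presented with baseline corrected". Note a to the Schedule of Activities takes serum albumin at screening and again pre-dose: "The two times serum albumin average will be used as" the subject's baseline. It does not mention PK. Section 11.4.1 specifies the NCA, a log-log regression of Cmax or AUC on dose, and a power model for dose proportionality. It does not mention baseline.

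**Serum albumin as an endpoint.** Section 3.2 lists as exploratory "Changes in serum albumin level and colloid osmotic pressure". The synopsis has serum albumin measured at baseline and at Table 1 time points. Table 1 has no row of that name, and the chemistry panel in footnote 10 does not include albumin.

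**The concern.** PK is a secondary objective, available PK data go to the escalation review (4.2.2), and the repeat-dose schedule is to be based on single-dose results (4.2). Section 2.1 calls albumin the main plasma protein, so a total-albumin assay reads far from zero before dosing. A slope of log exposure on log dose is then dominated by a constant that the drug did not supply, and CL, volume and half-life lose their usual meaning.

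The documents give some reason not to assume specificity:

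- An assay blind to endogenous albumin would not normally need the baseline correction that the synopsis plans.
- The rat PK work used a radiolabel to tell exogenous from endogenous albumin (2.3.2). No equivalent is described for this trial.
- OsrHSA is described as equivalent to plasma albumin in structure and immunogenicity (2.1), with shared epitopes (2.3.3).

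Leaving the choice between corrected and uncorrected data open also lets it be made after results are seen.

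**Working it through.** The plan gives no figure to reproduce. The first step is textual, and the rest is an illustration that applies only if total albumin is measured.

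**1. Side by side.**

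| Place | Analyte | Baseline correction |
|---|---|---|
| 1.1 Synopsis | albumin; also OsrHSA | additional presentation |
| Table 1, footnote 13 | serum albumin | not mentioned |
| 7.2 | OsrHSA, immunoassay | not mentioned |
| 11.4.1 | OsrHSA | not mentioned |

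**2. Inputs.** From the documents: doses of 20, 40, 80, 140 and 200 mg/kg; 6 active subjects per cohort; the sampling times in footnote 13. Assumed, not in the documents: baseline B 35-50 g/L, plasma volume V 40-50 mL/kg, AUC distribution volume 42-100 mL/kg, half-life 10-20 days, within-subject albumin SD 1-2 g/L. The true drug exposure is taken as exactly proportional to dose (slope 1).

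**3. Uncorrected Cmax** = B + dose/V (mg/kg divided by mL/kg is g/L). With B = 40 and V = 45, the increments are 0.44, 0.89, 1.78, 3.11 and 4.44 g/L. The totals run from 40.44 to 44.44, a 10% rise for a tenfold dose, and the log-log slope is 0.040. Over the ranges the slope runs from 0.029 (B = 50, V = 50) to 0.051 (B = 35, V = 40).

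**4. Uncorrected AUC0-30d** = 30B + (dose/V)(1 - exp(-30k))/k, with k = ln 2/half-life.

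- B = 35, V = 42, half-life 20 d, 200 mg/kg: 1050 + 4.762 x 18.65 = 1050 + 88.8, so 1050/1138.8 = 92.2% is endogenous. Slope 0.031.
- B = 50, V = 100, half-life 10 d, 200 mg/kg: 1500 + 2.0 x 12.62 = 1500 + 25.2, so 98.3% is endogenous. Slope 0.006.

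**5. Corrected data.** With a two-value baseline and independent errors, the error SD of one corrected value is SD x sqrt(1 + 1/2). The chance that the corrected EOI value is non-positive at 20 mg/kg is Phi(-(20/V)/(SD x sqrt(1.5))). For V = 40 and SD = 1 this is Phi(-0.408) = 34%. For V = 50 and SD = 2 it is Phi(-0.163) = 44%. Simulation (4,000 trials per setting, no dilution) gives:

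| Quantity | Non-positive at 20 mg/kg | Log slope, positive values only | Linear fit with intercept: slope/true, mean (SD) |
|---|---|---|---|
| EOI value (V 40-50) | 34-44% | 0.81 down to 0.40 | 0.99-1.00 (0.13-0.34) |
| AUC0-30d (V 42-100) | 36-48% | 0.75 down to 0.12 | 0.99-1.01 (0.15-1.06) |
| Observed Cmax (V 40-50) | about 1-2.5% | 0.54 down to 0.30 | 0.93 down to 0.83 |

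The mechanism differs by parameter. For the EOI value and AUC, the log model must discard the non-positive results, which are mostly at low doses. For observed Cmax almost nothing is discarded. There the maximum of 12 noisy post-dose values is biased upward, proportionately most at low doses.

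**The case against.** The best opposing case is that this is loose naming. OsrHSA is itself a recombinant human albumin, and the synopsis uses both terms within a few lines. An OsrHSA-specific assay would remove the numerical problem. That stands, and is why the size is conditional. A reader might infer that the trial measures total albumin. The documents point that way in places but do not say so.

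Three other stronger readings should be resisted:

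- **That corrected NCA parameters are not planned.** They are: the synopsis sentence follows directly on the NCA parameter list, and section 11.4.1 is silent rather than contradictory. What is missing is which version is primary and which feeds the power model.
- **That the exploratory albumin endpoint has no post-dose measurement.** Note a requires albumin at screening and pre-dose, and that has no row of its own in Table 1 either, so a missing row proves little. Both assays could also be run on one sample. The supportable statement is that the only post-dose source named is the PK sample in footnote 13.
- **That discarded non-positive values explain the flattening for Cmax.** They do not; the upward bias of the maximum does. For the same reason a linear fit does not rescue observed Cmax.

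It can also be said that PK is secondary, the sample size is not statistical, and AUC proportionality may remain imprecise after any fix. That limits the weight of the point but does not settle the open choice of data set.

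**Conclusion.** The point holds in a limited form. The analyte wording is inconsistent, assay specificity is unstated in the text available, and section 11.4.1 leaves open which version of Cmax and AUC is primary. None of this rests on assumptions.

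The size does, and it arises only with total albumin. Uncorrected slopes are then about 0.03-0.05 (Cmax) or 0.01-0.03 (AUC0-30d) where the truth is 1, and 92-98% of AUC0-30d at 200 mg/kg is endogenous. Moving to corrected values is necessary in that case but does not repair the log power model. If the assay is specific to OsrHSA, only the wording and the source of the exploratory albumin endpoint need attention. Confidence is medium, because the documents do not settle which case applies.

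**What to change.** 1. Reconcile the analyte wording in 1.1, Table 1 footnote 13, 7.2 and 11.4.1. State whether the assay separates OsrHSA from endogenous albumin, and name the post-dose source of the serum albumin endpoint in 3.2.
2. If it does not separate them, make baseline-corrected concentrations the main input to the NCA and the dose-proportionality analysis in 11.4.1, and show uncorrected albumin as the exploratory endpoint. Baseline and post-dose values should come from the same assay. Note a averages in a screening value, but footnote 13 lists no screening PK sample.
3. In that case, assess proportionality on AUC and a named EOI concentration, not observed Cmax, by a linear fit with intercept on the original scale that keeps non-positive values. Do not rely on the log power model for corrected data.
4. Report AUC to infinity, half-life, CL and Vz only where a corrected terminal phase is estimable.

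**Cost.** Wording changes, with no new post-dose samples. If screening albumin is run by another method, either that sample is re-assayed or note a is changed. A pre-dose value alone raises the SD of the EOI linear slope by sqrt(2/1.5) = 1.15, about 15%.

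**Downside.** Low-dose parameters may not be estimable. The SD of the linear-slope ratio is 0.13-0.34 for EOI and 0.15-1.06 for AUC, so AUC proportionality may be uninformative. Section 6.2.4 fixes the infused volume ("OsrHSA will be diluted with normal saline to a total volume of 200ml"). The intercept absorbs a constant dilution from it, but not one that grows with dose.
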